The goal of the project is to improve the care of veterans with mild traumatic brain injury (TBI) and alcohol use disorder (AUD). The PI and coinvestigator are conducting a pilot controlled clinical trial to assess the efficacy of N-acetylcysteine (NAC) to reduce alcohol use and improve brain injury symptoms in veterans with TBI who have AUD. This proposed project builds upon our current IMN-funded research on topiramate pharmacotherapy for unhealthy alcohol use in veterans with TBI.

Exposure to injuries and stresses of combat is known to be associated with risk for both traumatic brain injury and hazardous and harmful alcohol use. Veterans, especially those involved in the Iraq and Afghanistan conflicts (Operation Iraqi Freedom [OEF], Operation Enduring Freedom [OEF] and Operation New Dawn [OND] have high rates of TBI. Because of the adverse interaction of heavy alcohol use and TBI, there is a clinical need for effective treatments to reduce hazardous and harmful alcohol use in these veterans. The proposed project directly builds on the PI's current pilot controlled trial of topiramate in veterans with PTSD and alcohol dependence. Acetylcysteine (NAC) has been shown to be efficacious in the treatment of dependence and may also have benefit in the treatment of PTSD, which often accompanies TBI.

Over 2 million veterans have served in the Iraq and Afghanistan conflicts -- Operation Iraqi Freedom (OIF) and Operation Enduring Freedom (OEF) and 23%-30% may have sustained mTBI¹⁻³. The prevalence of alcohol and other substance use disorders in OIF/OEF veterans with TBI is approximately twice that of veterans without TBI^{1,4}. Although the majority of alcohol treatment studies have focused on AUD, the spectrum of unhealthy alcohol use includes both hazardous as well as harmful drinking. Hazardous alcohol use has been defined as drinking that exceeds recommended limits (≥14 drinks/week for men or 7 drinks/week for women or anyone over age 65) and is associated with higher prevalence of a wide range of medical and psychiatric morbidities. Harmful alcohol use is drinking that meets DSM-5 criteria for a diagnosis of AUD. Hazardous and harmful alcohol use (HHAU) is common among veterans; recent large epidemiologic studies found that 22-40% of OEF/OIF veterans screened positive for HHAU^{5,6}.

Neurocognitive impairment may be both an important contributor to, as well as a result of, alcohol use and TBI. AUD is associated with, or causal to, a wide variety of neurobehavioral harms. These include impulsivity, risk-taking behavior, irritability/mood instability, depression, and suicide risk. HHAU is also associated with deficits in executive functioning, learning, memory, and decision making, with increased impulsivity and risk-taking. Both HHAU's and TBI's association with impairments in self-control and decision-making are linked to ventromedial and orbitofrontal cortex dysfunction. Thus, both TBI and HHAU may independently and additively alter cognitive, emotional, and behavioral functioning. These alcohol- and TBI-related impairments can also synergistically increase the potential for risk-taking and contribute to many of the harmful behaviors seen in veterans with HHAU and TBI. By extension, they also affect their families, and the community at large.

NAC has been proposed as a neuroprotective agent that may benefit TBI, mediated through antioxidant and anti-inflammatory effects⁷ and it may assist in reducing alcohol use. Reducing alcohol use and improving brain injury symptoms via NAC treatment may have the potential to improve cognitive functioning and reduce risky behavior in veterans with TBI. Reducing impulsivity and risk-taking propensity can be expected to reduce harmful behaviors that are tied to poor adherence to medical care, marital relationship problems, domestic and other forms of violence, and suicide. If, as expected, NAC treatment improves the management of TBI and AUD, it would have unambiguous benefits both for active duty military personnel and veterans.

Improving the care of veterans with TBI and unhealthy alcohol use is likely to help families and communities affected by the sequelae of these problems. Moreover, treatments that help veterans with TBI and unhealthy alcohol use are likely to be applicable to the general population of individuals with these comorbid problems.

The objectives of the study are: (a) to successfully recruit 30 veterans with mild TBI and hazardous or harmful alcohol use; (b) to test primary and exploratory hypotheses as described below.

Outcomes, products and deliverables: Outcomes: The primary treatment outcome will be percent heavy drinking days of alcohol per week. The secondary outcome will be TBI symptom severity as measured by the Neurobehavioral Symptom Inventory (NSI). The exploratory outcomes will be levels of executive functioning (impulsivity, risk-taking, and decision making) and other neurocognitive domains assessed over the course of the study. *Products:* Data will be collected on 8 weeks of treatment plus week 12 follow-up. *Deliverables:*

This study is being sponsored by the Department of Defense (DOD) Telemedicine and Advanced Technology Research Center (TATRC).

II. RESEARCH PLAN

A. GOALS AND SPECIFIC AIMS

The overall goal of the project is to improve the care of veterans with traumatic brain injury and unhealthy alcohol use. We will conduct a pilot controlled clinical trial to assess the efficacy of N-acetylcysteine (NAC) to reduce alcohol use and improve brain injury symptoms in veterans with TBI who consume alcohol at *hazardous or harmful* levels. This project builds upon our current ITN-funded research on topiramate pharmacotherapy for unhealthy alcohol use in veterans with TBI.

A.1. PRIMARY AIMS:

Aims:

Measure both alcohol use and TBI symptom severity over the course of the 12-week study in order to detect differential efficacy of NAC and placebo. Alcohol use treatment outcome will be the Percent Days of Heavy Drinking (PHDD) of alcohol

A heavy drinking day is defined using NIAAA (2007) criteria: any day with 5 or more drinks per day for men or 4 or more drinks per day for women⁸. The choice of PHDD as the primary outcome is based on its endorsement by a recent NIAAA consensus conference⁹ and its increasing use in clinical trials ¹⁰⁻¹². TBI symptom severity will be measured with the Neurobehavioral Symptoms Inventory (NSI)^{13,14} a measure of postconcussive symptom severity.

Hypotheses:

Our **two primary** aims examine group differences, to detect differential efficacy of NAC vs placebo (*between-group analyses*). We will test the following hypotheses with between-groups analyses:

- NAC treatment combined with Medical Management (MM) alcohol counseling will have greater efficacy than placebo in reducing percent heavy drinking days (PHDD). A heavy drinking day is defined using NIAAA (2007) criteria: any day with ≥5 drinks for men or ≥4 for women⁸. PHDD as primary outcome is based on recent NIAAA consensus⁹ and increasing use in clinical trials¹⁰⁻¹².
- **2.** NAC treatment will have a greater efficacy than placebo in reducing TBI related symptoms. TBI symptom severity will be measured by the Neurobehavioral Symptom Inventory (NSI)^{13,14}.

A.2. EXPLORATORY AIMS:

Exploratory Aims:

Other exploratory aims will include obtaining additional measures of alcohol use, executive functioning (e.g., impulsivity and risk taking) and other domains of neurocognition, and examining the potential moderating effect of rs6465084 on NAC treatment response

Hypotheses:

NAC treatment will have greater efficacy than placebo in: a) reducing other alcohol use measures (percent drinking days per week, drinks/week, drinks/drinking day, alcohol craving, biomarkers); b) improving neurocognition. We will examine neurocognitive domains which include executive functioning (impulsivity, risk-taking, decision making), auditory-verbal learning and memory, verbal fluency, processing speed and working memory. We will also explore the potential moderating effect of rs6465084 on NAC treatment response.

A.3. FUTURE PLANS

If the results of this pilot NAC HHAU/TBI project are positive, the investigators will seek funding for a larger controlled trial through the Department of Defense CDMRP and related funding programs and/or NIAAA R01 mechanisms. We believe that we can derive a reliable estimate of effect size for planning a randomized controlled trial from this small parallel groups controlled pilot study. It will be useful to obtain estimates of

variability for the key outcome variables in this population of comorbid patients in order to inform future controlled trials. Furthermore, we would seek to partner with other investigators in future studies to include neuroimaging to examine potential pre to post treatment neurobiological changes which may occur with NAC treatment.

B. BACKGROUND AND SIGNIFICANCE

B.1. OVERVIEW

To achieve these aims, we will conduct a pilot prospective, parallel groups, randomized, double-blind, placebocontrolled flexible-dose clinical trial of NAC in 30 veterans with TBI and hazardous or harmful alcohol use. The 8-week treatment phase will consists of treatment with NAC or placebo, plus weekly manualized alcohol counseling, added to whatever usual TBI treatment participants may be receiving, including medication (exceptions being any alcohol treatment medications). The manualized counseling for alcohol use disorders will consist of Medical Management¹⁵, an NIAAA manual-driven, low-intensity supportive program to promote adherence to the medication regimen and retention. Participants will continue to receive usual care for TBI and other medical and/or psychiatric disorders from their primary medical and mental health treatment providers. Participants will meet with research staff weekly to receive medication, counseling, and research assessments during the 8 weeks of study treatment. Participants will also be assessed at the week-12 follow-up visit.

B.2. THE CO-OCCURRENCE OF TBI AND HAZARDOUS AND HARMFUL ALCOHOL USE AMONG VETERANS

Over 2 million veterans have served in the Iraq and Afghanistan conflicts -- Operation Iraqi Freedom (OIF) and Operation Enduring Freedom (OEF) and 23%-30% may have sustained traumatic brain injury (TBI)¹⁻³. Evidence indicates that the prevalence of alcohol and other substance use disorders in OIF/OEF veterans with TBI is approximately twice that of veterans without TBI^{1,4,16,17}. Post TBI, more service members have diagnoses of alcohol/substance abuse than any other selected condition except headache¹⁸. Evidence suggests that TBI may play a causal role in this relationship. For example, in a recent study, airmen with TBI were shown to have an increased risk for addiction-related disorders compared with a similarly injured non-*TBI* comparison group. The hazards for alcohol dependence and nondependent abuse of drugs or alcohol were significantly elevated in those with TBI as compared to controls¹.

B.3. UNHEALTHY ALCOHOL USE: HAZARDOUS AND HARMFUL ALCOHOL USE

Although the majority of alcohol treatment studies have focused on alcohol use disorder (AUD), the spectrum of unhealthy alcohol use includes hazardous as well as harmful drinking. Hazardous alcohol use has been defined as drinking that exceeds recommended limits (≥14 drinks/week for men or 7 drinks/week for women or anyone over age 69)^{8,19} and is associated with higher prevalence of a wide range of medical and psychiatric morbidities⁸. Harmful alcohol use is alcohol use that meets DSM-5 criteria for a diagnosis of AUD²⁰. Hazardous and harmful alcohol use (HHAU) is common among veterans; recent large epidemiologic studies found that 22-40% of OEF/OIF veterans screened positive for HHAU^{5,6}.

B.4. NEUROBEHAVIORAL INTERACTIONS OF HEAVY ALCOHOL USE AND TBI

Both TBI and HHAU are associated with impulsivity and impaired decision-making and linked to ventromedial and orbitofrontal cortex dysfunction²¹. Both TBI and HHAU are also associated with, or causal to, a wide variety of neurobehavioral harms. These include impulsivity, irritability/mood instability, depression, and suicide risk. Other impairment occur in attention, concentration, visual-spatial memory, and executive functioning -- including decision-making, risk-benefit analysis, and behavioral inhibition²². TBI and HHAU can synergistically increase the potential for these cognitive, emotional, and behavioral impairments and thereby increase risk-taking behavior.

Neurocognitive functioning has been shown to be an important moderator of substance abuse treatment outcome^{21,23}. Neurocognitive impairment may therefore be both an important contributor to, as well as a result of, continued alcohol use in TBI. However, cognitive functioning has been shown to improve even after brief periods of abstinence from alcohol²¹. Reducing alcohol use may thus have the potential to improve cognitive functioning, improve decision-making and reduce risk-taking behavior in veterans with TBI.

B.5. LIMITS OF CURRENT PHARMACOTHERAPIES FOR AUD AND FOR HHAU IN TBI

Although there are several FDA-approved medications for the treatment of AUD, no consensus exits regarding medications to reduce hazardous alcohol use, and there are no published reports of pharmacotherapies for either AUD or other forms of HHAU in patients with TBI. Disulfiram, acamprosate, as well as oral and extended-release injectable forms of naltrexone are approved by the Food and Drug Administration (FDA) for the treatment of AUD. Topiramate is also an efficacious medication although not FDA-approved for AUD. However, these medications have limitations and at best show only modest to moderate efficacy²⁴. The most rigorous controlled trial of disulfiram showed only questionable efficacy²⁵ and disulfiram treatment requires abstinence from alcohol. Naltrexone studies have generally supported its efficacy reducing drinking, although effect sizes are modest²⁴. Naltrexone's opioid antagonism precludes its use in patients who require opioid analgesic treatment, a salient issue for many injured veterans with chronic pain conditions. Acamprosate has been found to reduce alcohol relapse rates in European studies²⁶, however, trials conducted in the United States, e.g. the COMBINE²⁷ study, have failed to establish its efficacy in intent-to-treat analyses. Disulfiram and oral naltrexone also have hepatotoxic potential, although low. The available treatments also have other clinically significant adverse effect burdens. Topiramate treatment, for example, as demonstrated by the PI's previous research (see below) is associated with cognitive impairment in veterans with AUD, a problem of particular relevance to individuals with TBI. Other difficulties with these medications are cost, with acamprosate and injectable naltrexone being the most costly. There is therefore a need to find novel alternative, safe, well-tolerated, and low-cost medications for the treatment of AUD, and in particular, for the treatment of HHAU in veterans with TBI.

C. PRELIMINARY STUDIES

C.1. N-ACETYLCYSTEINE BACKGROUND AND EVIDENCE FOR USE IN DISORDERS OR ADDICTION

N-Acetvlcvsteine (NAC) is FDA-approved, most commonly used as a mucolytic²⁸ and in the treatment of acetaminophen overdose²⁹. NAC's potential as a treatment for substance use disorders is related to its roles in oxidative homeostasis and glutamate activity³⁰. NAC is the acetylated precursor of the amino acid L-cysteine, and although it has a relatively low bioavailability (below 5%), NAC associated redox exchange reactions produce cysteine, which can cross the epithelial cell membrane and blood brain barrier in abundance³¹. Cysteine is involved in the synthesis of glutathione (GSH), a tripeptide composed of glutamate, cysteine and glycine, which serves as a ubiquitous antioxidant neutralizing oxidative free radicals³². NAC-derived cysteine also assists in the regulation of Glu through the cystine-Glu antiporter³⁰. NAC increases activity of the catalytic subunit of the cysteine-Glu exchanger and Glu transporter 1 (GLT1)³³⁻³⁵. Through this system, glial astrocytes exchange cysteine for Glu, which is released into the extracellular space inducing an increase in the glutamatergic tone on presynaptic metabotropic Glu receptors 2/3 (mGluR2/3)³⁶, which in turn has an inhibitory effect on presynaptic glutamate release³⁶. Both *acute* and *chronic* alcohol consumption has been shown to increase extracellular levels of glutamate in the nucleus accumbens (NAcc)^{37,38}. Extracellular Glu in the NAcc is associated with cue-induced reinstatement of alcohol-seeking behavior³⁹. The alcohol-induced dysregulation of extracellular Glu is likely due to an alteration in the mechanism of relase and reuptake of Glu similar to that shown in cocaine addiction⁴⁰⁻⁴⁵. With repeated exposure to cocaine, extracellular Glu is reduced in the NAcc via decreased tonic activation of relase-regulating mGlu2/3^{38,41,46-48}. Modulation mGluR2/3 cysteine-Glu exchange via NAC restores basal extracellular levels of Glu and prevents cocaine^{40,49,50} and heroin^{51,52} seeking. More importantly, reduction in glutamatergic transmission via activation of mGlu2/3 attenuates alcohol seeking behavior^{53,54}. In sum, NAC may regulate elevated extracellular glutamate³⁶ resulting from acute and chronic alcohol exposure⁵⁵, thus repairing faulty communication between NAcc and prefrontal cortex⁵⁶.

Medications that modulate the effects of Glu in the midbrain have shown clinical effectiveness in the treatment of AUD⁵⁷⁻⁵⁹. Additionally, animal models have demonstrated the ability of GSH to potentiate N-methyl-D-aspartate receptor response to Glu³⁰. NAC can aid in the synthesis of GSH and it also simultaneously modulates dopamine (DA) transmission and DA-associated reactive oxygen species⁶⁰. Medications that modulate Glu may suppress conditioned cue responses to alcohol after short-term abstinence⁶¹, reduce aversive effects of alcohol withdrawal related to increased Glu and decreased central DA levels, particularly in the nucleus accumbens^{62,63}, and inhibit neuronal hyperexcitability⁶⁴ following withdrawal^{65,66}. Moreover, NAC's

anti-inflammatory effects have also been implicated as playing a role in its potential therapeutic effects on the pathophysiology of substance use disorders⁶⁷.

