Random assignment will be followed by 8 weeks of treatment with NAC or placebo. Study medications will be identical in appearance. Participants will be provided with 10 days of medication at each weekly visit to increase the likelihood of medication continuity in case of a missed visit. Extra medication will be collected from participants at each visit. Study medication (NAC or placebo) will be started at a dose of 600 mg bid (1200 mg per day), for 3 days, then 1200 mg bid for 4 days, (2400 mg per day), then 1800 mg bid (3600 mg per day) for weeks 2 through 8. Similar doses have been shown to be an effective dose in other addiction studies (see A.2.). If the participant experiences significant side effects during the titration period, the dosage may be adjusted as necessary. Patients will be treated with the highest dose tolerated, not to exceed a total of 3600 mg per day, but may be reduced by 600mg increments as needed. Wellspring Compounding Pharmacy, a compounding Pharmacy – a compounding pharmacy recommended by the University of California, San Francisco School of Medicine Pharmacy -- will supply NAC study capsules and matching placebo capsules. The policies and procedures concerning good compounding practices and environmental, instrumental and procedural quality assurance have been approved by the California State Board of Pharmacy. The SFVAMC Research Pharmacist will directly receive all study medications from Wellspring Compounding Pharmacy and store in appropriate environmental conditions. The dosage is to be determined by a study physician at each weekly visit, using the titration schedule as a guide. An official VA prescription form must be filled out by a study physician for each patient at each visit. A research associate will pick up the prescription from the SFVAMC pharmacy. The date, time and amount of study compound dispensed will also be recorded in the subject's electronic medical file. Participants are instructed to return all unused study medication weekly. The number of returned capsules will be documented.

D.3.h. Medical Management

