Efforts will be made toward reducing the amount of missing data by: (a) use of a collateral informant to assist in locating patients; (b) telephone follow-up to make contact with missing patients; (c) establishment of flexible, but acceptable, time periods for the completion of each assessment; and (d) some self-report and interview measures may be administered by telephone to collect missing data from patients unwilling or unable to visit research sites to participate in a scheduled assessment session. All phone visits will include a Medical Management counseling session, during which a trained psychologist or psychiatrist (the Medical Manager) will assess adverse effects, concomitant medications, suicidality and general well-being. During phone visits, study coordinators will skip the question on the Adverse Event checklist, "Have you had suicidal thoughts or actions since the last study visit". Instead, the Medical Manager will ask that question and report back to coordinator after the Medical Management counseling session. If a Medical Management counseling session becomes logistically impossible, the PI will file a protocol violation.

Establishment of flexible, but acceptable time frames for completion of research assessments: All research assessments should be completed within an established window. Assessments scheduled for weeks 1, 2,3,5, 6, and 7 will have a window of ± 3 days for completion. Assessments scheduled for weeks 4, 8, and 12, have a window of ± 1 week for completion. This flexibility will enhance the ability of staff to schedule patients for assessments as close as possible to the protocol defined period. Patients likely to miss appointments should be scheduled early in the window to allow for successive attempts to complete ratings within the desired time frame.

After receiving CHR and R&D approval, we will be converting most of our questionnaire measures to a digital format, so that this questionnaire data can be collected and managed using the San Francisco VA Medical Center's Stress and Health Research Program Data Management Research Database System.

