Alcohol and drug use will be assessed using the Time-Line Follow-Back (TLFB)_1^{135,136}. This is a self-report test which will be performed at baseline/screening and will cover the 12 weeks prior to entry, with particular attention to the 4 weeks immediately preceding entry to the study. In addition, the TLFB will be done weekly for the preceding 7 days at weeks 1-8, and at week 12. The TLFB will be used to calculate percent of days abstinent from alcohol, drinks per drinking day, and percent heavy drinking days. The (TLFB) is a method to assess the quantity of alcohol consumption on a daily basis. With a calendar as a guide, the participant provides a retrospective estimate of daily drinking over a specified period. For this study participants will estimate their daily drinking for the 28-day period prior to the initial screening and for the 7-day period prior to each weekly visit. The TLFB provides a calendar of the targeted period for recording the number of standard drinks consumed on each day. The TLFB can be used to obtain the number of days on which drinking occurred and the number of drinks per day. Standard Drink Conversions will be used to standardize all participant reports of alcohol consumption ⁸.

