Percent Heavy Drinking Days (PHDD): Negative binomial regression accommodates over dispersion and derives as an alternative to Poisson regression (most natural for analyzing count data). Heavy percent drinking days is often over-dispersed, positively skewed count data. Therefore, we will use random-intercept zero-inflated negative binomial model, modeling week (week 1 - week 8) as a continuous variable to analyze group differences in PHDD. *Neurobehavioral Symptom Inventory (NSI):* We will use random-intercept linear mixed models to explore the efficacy for NAC related reduction in TBI symptom severity measured by the NSI. Time period will be treated as a repeated effect, with correlations between time periods within participants modeled by an unstructured correlation matrix where appropriate. Model assumptions will be tested and required modifications will be performed. Both models will included fixed effect for week, treatment group (NAC and placebo), and the interaction between treatment group and week. Baseline alcohol consumption and NSI means will be used as respective covariates in group comparisons to control for pre-study and study enrollment effects.

3) Power Analyses for the Primary Outcome

We conducted a power analysis on our current pilot study of topiramate treatment of *alcohol dependence* in veterans with PTSD (see Section C.2.b.). For the outcome measure of percent drinking days (PDD), the effect size from the pilot data comparing week 12 to baseline within the topiramate group is d = 1.87. Because the proposed project is focused on veterans with TBI who have *hazardous* as well as harmful alcohol use, rather than just harmful use (alcohol dependence), we assume that the participants may start at a lower baseline level of DD in the proposed study than in the pilot study. This may not allow us to show as much improvement in the proposed study as in the completed pilot study of PTSD and alcohol dependence. Therefore, it would seem reasonable to target an effect size approximately half of what we found in our pilot study, i.e. d=0.9. A sample size of 16 for the topiramate arm of our proposed placebo-controlled pilot will allow us to detect a within-subjects effect size of d = 0.9, with 80% power at alpha = .05.

D.6.b. Exploratory outcomes/exploratory hypotheses

1) Exploratory Hypotheses

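### Weekly heavy-drinking percentages follow the visit date, not the study week, so off-schedule visits can put pre-treatment, post-week-8 and repeated days into the primary analysis

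*Combined protocol and SAP*

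**What the plan says.** The Synopsis defines the primary outcome by the week: it "will be percent heavy drinking days of alcohol per week". D.4.d.1 derives it from the Timeline Followback (TLFB) and states twice that recall is tied to the visit: "the TLFB will be done weekly for the preceding 7 days at weeks 1-8, and at week 12", and again "for the 7-day period prior to each weekly visit".

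D.4.a sets the visit windows: "Assessments scheduled for weeks 1, 2,3,5, 6, and 7 will have a window of ± 3 days for completion", and "Assessments scheduled for weeks 4, 8, and 12, have a window of ± 1 week for completion". It adds: "Patients likely to miss appointments should be scheduled early in the window".

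The primary model, given in D.6.a and in the statistical plan under D.3.i, is a random-intercept zero-inflated negative binomial model, "modeling week (week 1 - week 8) as a continuous variable to analyze group differences in PHDD". On treatment length, D.3.g says: "Random assignment will be followed by 8 weeks of treatment with NAC or placebo".

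D.4.d.1 gives the denominator only as the number of study days, without defining it. Its one recall rule that avoids both overlap and gaps, from the last visit to the present one, is written for cigarettes and non-alcohol substances.

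**The concern.** The recall period is fixed at 7 days while the interval between visits is not. When a visit moves, its 7-day record moves too, but the record keeps its nominal week number in the model. Three kinds of day can then enter under the wrong week: days before first dose in the week-1 record, days after the 8 treatment weeks in the week-8 record, and days already counted at the neighbouring visit. Nothing in D.4.d.1, D.3.i or D.6.a reassigns or removes them.

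At stake are the size of the treatment effect and its change over weeks. The pilot is meant to supply effect-size and variability estimates for a larger trial (A.3 and D.3.i), so dilution carries into that planning. Visit timing may also depend on drinking. D.4.d.3 requires a breath alcohol reading of zero for neurocognitive visits, otherwise the visit waits or moves to another day. Those visits are weeks 4, 8 and 12, which have the widest windows.

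**Working it through.** The plan gives no figure of its own on this point. The check is day arithmetic.

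**Conventions (assumed).** First dose is day 1, treatment is days 1-56, and visit k is nominally day 7k. A visit on day v yields a record of days v-6 to v.

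**Extremes**
- Week 1, 3 days early: day 4, covering days -2 to 4. Days -2, -1 and 0 precede first dose: 3/7 = 43%.
- Week 8, 7 days late: day 63, covering days 57-63. All 7 fall after day 56.
- Two visits g days apart (g < 7) share 7 - g days. One visit 3 days early repeats 3 days. A week-4 or week-8 visit 7 days early lands on nominal day 21 or 49 and repeats the whole week-3 or week-7 record.
- Most days outside treatment: 3 + 7 = 10 of 56 (17.9%).

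**Average counts per participant.** Pre-dose and post-day-56 means for independent uniform timing are exact: (1+2+3)/7 = 0.86 and (1+...+7)/15 = 1.87 over the full windows, and 1/3 each within ±1 day. Repeated and uncollected days come from simulation. Ranges show visits forced into order versus left independent.

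| Timing (assumed) | Pre-dose | After day 56 | Repeated | Treatment days not collected |
|---|---|---|---|---|
| On schedule | 0 | 0 | 0 | 0 |
| Uniform within ±1 day | 0.33 | 0.33 | 3.1 | 3.8 |
| Uniform over full windows | 0.86 | 1.87 (2.1 if in order) | 9.3-10.1 | 12.2-12.8 |

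**Group-by-week slope.** Assume the true effect in week k is k/8, with none before dosing or after day 56. Centred weeks run from -3.5 to 3.5 with sum of squares 42, and the true least-squares slope is 1/8. Let p be the pre-dose share of week 1 and q the post-day-56 share of week 8. The slope becomes 1/8 + 3.5p/(8×42) - 3.5q/42, so

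relative loss = 2q/3 - p/12.

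- ±1 day: p = q = 0.333/7 = 0.0476. Loss = 0.0317 - 0.0040 = 2.8%.
- Full windows: p = 0.857/7 = 0.1224, q = 1.867/7 = 0.2667. Loss = 0.1778 - 0.0102 = 16.8%.

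If days in every record also carry the effect of the week they belong to, the losses are about 4% and 20-21%. That gives ranges of 3-4% and 17-21%. The minus sign on p matters: pre-dose days in week 1 lower the smallest effect and slightly steepen the slope, so the flattening comes mainly from week 8.

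**Mean effect, weeks 1-8.** The weekly effects sum to 4.5, so the relative loss is (p/8 + q)/4.5.
- ±1 day: (0.0060 + 0.0476)/4.5 = 1.2%.
- Full windows: (0.0153 + 0.2667)/4.5 = 6.3%.

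**Drug supply.** D.3.g dispenses 10 days of medication per visit. Week-7 visits on days 46, 49 and 52 give supply to days 56, 59 and 62. Of days 57-63, then, 7, 4 or 1 lie beyond the supply. The assumption that all effect is lost after day 56 therefore makes the slope losses upper values for a given timing.

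**Precision.** As a rough linear approximation, treat each record as the mean of 7 independent daily values around the participant's own level. Two records sharing m days then have covariance m/49 times the daily variance, which a random intercept does not represent. The model-based slope standard error comes out about 4-5% too small within ±1 day and 13-15% too small over the full windows. This is indicative only, because the planned model is not linear.

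**The case against.** The strongest reply is that this is a possibility, not a stated outcome. D.4.a aims for visits close to the planned date. D.4.d.1 requires a prepared calendar, a diary card and discussion of discrepancies, and no section says that an overlapping date is to be entered twice. A careful analyst might reconcile the dates. That stands as far as certainty goes: nothing goes wrong when visits are on time. It does not remove the gap, because the only recall rule written for alcohol is the visit-anchored one.

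Uniform timing over the full windows is also a wide-scatter case. With independent dates, about 27% of such schedules put consecutive visits on the same day or out of order, which sits badly with weekly dispensing. The ±1-day row belongs beside it.

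A reader might infer more than the documents support:
- **That the slope loses two thirds.** Setting q = 1 and p = 0 gives 2/3, but only if every week-8 visit is 7 days late and all effect stops on day 57.
- **That pre-dose days in week 1 flatten the slope.** Under the linear model they do not; they dilute the mean effect.
- **That repeated records are analysed as independent.** The model has a random intercept. What it misses is the extra correlation from shared days.
- **That the problem falls on poor attenders.** D.4.a books them early to leave room for further attempts, so a missed early slot yields a later visit.
- **That one arm is favoured.** The windows are the same in both blinded arms. Timing may depend on drinking, but no directional bias is shown.

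**Conclusion.** The point holds as a derivation gap. Followed as written, the plan can place pre-dose, post-day-56 and repeated days in the primary analysis under the wrong week whenever visits are off schedule. The size depends on visit timing, which the documents do not give. It runs from nothing, through about 3 repeated days of 56 and a 3-4% slope loss within ±1 day, to about 9-10 repeated days and a 17-21% loss under uniform full-window timing. The slope figures rest on an effect that grows linearly and ends at day 56, and on the day numbering assumed above. The expected harm is dilution and a somewhat understated slope standard error. It does not invalidate the trial, but it is cheap to prevent and worth correcting.

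**What to change.** In D.4.d.1 and D.6.a, and in the matching text of D.3.i, derive weekly PHDD from the dated TLFB days by study day:

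- Study week k is days 7(k-1)+1 to 7k from first dose.
- Each calendar day is counted once.
- Days before first dose belong to baseline; days after day 56 belong to follow-up.
- The number of recorded days in the week is the denominator, or enters the model as an offset.
- A study week with no recorded days is missing in the mixed model.

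The cost is wording and programming, since the TLFB is already a daily calendar. Visits and windows stay as they are.

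The downside is incomplete weeks. If the 7-day recall is kept, uniform full-window timing leaves about 13 treatment days per participant uncollected and about 12% of participants with at least one empty study week. Within ±1 day about 4 days are lost and no week is empty, because each visit still covers at least 6 days of its own week. Extending the alcohol TLFB to the since-last-visit recall already used for other substances would close these gaps. Days between an early week-8 visit and day 56 would then be captured at week 12, if that visit is attended. The price is a longer recall at some visits.
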